11.0 Safety Analysis

11.1 General Considerations

Safety analyses will be performed on the safety population for data corresponding to DB treatment and on the OL population for data corresponding to OL treatment. Safety data will be summarized for the set of all subjects and for the geographic region of China.

For safety analyses, data from the active (Arm A) and placebo (Arm B) treatment arms during the DB Treatment Period will be summarized, and comparisons between Arms A and B will be performed, as appropriate. Data from the PT Period for Arm A through PT Week 4 will also be summarized for the change from baseline analyses of laboratory parameters, and through PT Week 24 for the change from baseline analyses of vital sign parameters.

Data from the OL Treatment Period and PT Period for Arm B will be not be summarized in the primary CSR, except listings of any serious adverse events and deaths from the OL Treatment Period for Arm B will be included in the primary CSR; these data will be summarized in the interim analysis (following the primary CSR) and in the final CSR.

11.2 Analysis of Adverse Events

Adverse events (AEs) will be coded using the MedDRA coding dictionary. The actual version of the MedDRA coding dictionary will be noted in the CSR.

HIV-1-infected subjects participating in clinical trials may develop infections typically associated with AIDS. A list of these known AIDS-associated opportunistic infections (OIs) is contained in Appendix D of the study protocol. AEs that are identified by the

investigators as AIDS-associated OIs will not be included in any analyses of AEs, but will be summarized separately for the HCV/HIV co-infected subjects.

11.2.1 Treatment-Emergent Adverse Events

Treatment-emergent AEs are defined below for the DB and OL Treatment Periods separately.

Treatment-Emergent AEs in DB Treatment Period

For the active arm (Arm A), treatment-emergent AEs are defined as any event with an onset date that is after the first dose of active study drug and no more than 30 days after the last dose of study drug. For the placebo arm (Arm B), treatment-emergent AEs are defined as any event with an onset date that is after the first dose of placebo through 30 days after the last dose of placebo and prior to OL Day 1 (if applicable). Events where the onset date is the same as the study drug start date are assumed to be treatment-emergent. If an incomplete onset date was collected for an AE, the event will be assumed to be treatment-emergent, unless there is other evidence that confirms that the event was not treatment-emergent (e.g., the event end date was prior to the study drug start date).

Treatment-Emergent AEs in OL Treatment Period

For subjects in the OL Population, treatment-emergent AEs are defined as any event with an onset date that is after the first dose of OL study drug and no more than 30 days after the last dose of OL study drug. Events where the onset date is the same as the OL study drug start date are assumed to be treatment-emergent. If an incomplete onset date was collected for an AE, the event will be assumed to be treatment-emergent, unless there is other evidence that confirms that the event was not treatment-emergent (e.g., the event end date was prior to the OL study drug start date).

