### **5.1.3 Open-Label Treatment Period**

After completing the DB Treatment Period, subjects initially randomized to placebo (Arm B) at the beginning of the DB Treatment Period will receive 8 or 16 weeks of open-label ABT-493/ABT-530. Subjects will be provided dosing instructions and will be dispensed study drug at the final scheduled DB Treatment Period visit (Week 8 or Week 16). Administration of ABT-493/ABT-530 will start the next day (OL Day 1). The same type of bottles as used for placebo will be used for active study drug ABT-493/ABT-530.

Sites must call subjects within 4 days after the final scheduled DB Treatment Period visit (Week 8 or Week 16) to verify the first day of open-label, study drug administration and record this date on the eCRF and in the source documents. Study drugs, virologic results and safety laboratory results will not be blinded during the OL Treatment Period. Virologic failure criteria and toxicity management will be evaluated and applied by the investigator (Section 5.4.1.1 and Section 6.1.7).

Subjects who prematurely discontinue from the OL Treatment Period should return for a Treatment D/C Visit and undergo the study procedures as defined in Appendix C and as described in Section 5.4.1. Ideally, this should occur on the day of study drug discontinuation, but is recommended to be no later than 2 days after their final dose of study drugs and prior to the initiation of any other anti-HCV therapy. Subjects who complete or discontinue the OL Treatment Period will be monitored for safety, HCV RNA, the emergence and persistence of resistant viral variants, plasma HIV-1 RNA and HIV resistance (as applicable) in the 24-week Post-Treatment Period as detailed in Section 5.1.4.

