### **8.1.5.1 Adverse Events**

Adverse events (AEs) will be coded using the Medical Dictionary for Regulatory Activities (MedDRA). AE data will be summarized and presented using primary MedDRA system organ classes (SOCs) and preferred terms according to the version of the MedDRA coding dictionary used for the study at the time of database lock.

AEs will be presented for the following treatment groups: (1) double-blind active (Arm A in the DB Treatment Period), (2) double-blind placebo (Arm B in the DB Treatment Period), and (3) open-label active (OL Population Arm B). Treatment group comparisons refer to comparisons of events between double-blind active and double-blind placebo during the DB Treatment Period of the study. For the active treatment arm during the DB Treatment Period (Arm A), treatment emergent AEs are defined as any event that begins or worsens in severity after initiation of active study drug through 30 days after the last dose of active study drug. For the placebo arm (Arm B), treatment-emergent AEs during the DB Treatment Period are defined as any event that begins or worsens in severity after initiation of placebo through 30 days after the last dose of placebo and prior to OL Day 1 (if applicable). For subjects in the OL Population, treatment-emergent AEs are defined as any event that begins or worsens in severity after initiation of open-label study drug through 30 days after the last dose of open-label study drug.

The number and percentage of subjects in each treatment group with treatment-emergent AEs will be tabulated by primary MedDRA SOC and preferred term; comparisons between arms will be made using Fisher's exact test. The tabulation of the number of subjects with treatment-emergent AEs by severity grade and relationship to study drug DAAs also will be provided. Subjects reporting more than one AE for a given MedDRA preferred term will be counted only once for that term using the event with the most severe grade for the severity grade tables and the most related event for the relationship to study drug tables. Subjects reporting more than one type of event within a SOC will be counted only once for that SOC.

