4.2 Design Diagram

This is a Phase 3, randomized, double-blind, placebo-controlled multicenter study to evaluate the efficacy and safety of ABT-493/ABT-530 in non-cirrhotic chronic HCV GT1 to GT6-infected Asian adult subjects with or without HIV co-infection who are HCV treatment-naïve or treatment-experienced with IFN (alpha, beta or pegIFN) with or without RBV OR sofosbuvir with RBV with or without IFN. This study consists of a Double-Blind (DB) Treatment Period, an Open-Label (OL) Treatment Period, and a Post-Treatment (PT) Period. The study schematic is presented in [Figure 1](#).

The study is designed to enroll approximately 504 subjects to meet scientific and regulatory objectives without enrolling an undue number of subjects in alignment with scientific and ethical considerations. A minimum of 150 GT1-infected subjects, a minimum of 150 GT2-infected subjects and approximately 60 GT3, 4, 5 or 6-infected subjects from China will be enrolled into this study. Approximately 105 GT1-infected subjects and approximately 39 GT2-infected subjects will also be enrolled into this study from the regional Asian countries of South Korea and Singapore. Of the approximately 504 subjects, a maximum of 50 HCV/HIV co-infected subjects will be enrolled.

Figure 1. Study Schematic

Chronic HCV GT1 – 6 infected adults without underlying cirrhosis will be enrolled into one of two treatment arms:

Arm A: ABT-493/ABT-530 300 mg/120 mg QD for 8 or 16 weeks

Arm B: Matching Placebo for 8 or 16 weeks followed by open-label ABT-493/ABT-530 300 mg/120 mg QD for 8 or 16 weeks

All subjects in this study are to be non-cirrhotic. Treatment experienced GT3-infected subjects will receive 16 weeks of treatment in the DB and/or OL Treatment Period; all other subjects will receive 8 weeks of treatment in the DB and/or OL Treatment Period.

In China, subjects will be randomized to receive active treatment (Arm A) or placebo (Arm B) in a 2:1 ratio for each of the GT1 and GT2-infected groups and the combined GT3 to GT6 infected group. In each regional Asian country, each of the GT1 and GT2 infected groups will be randomized in a 2:1 ratio.

Subjects who are randomized to Arm B will receive open-label ABT-493/ABT-530 300 mg/120 mg QD for 8 or 16 weeks following the DB Treatment Period.

Randomization of subjects will be stratified by geographic region (China, Singapore and South Korea), genotype (GT1, GT2, combined GT3 – 6), and HCV/HIV co-infection status (yes, no).

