- Serious treatment-emergent AEs with a "reasonable possibility" of being related to DAAs (ABT-493/ABT-530);
- Treatment-emergent AEs of Grade 3 or higher;
- Treatment-emergent AEs of Grade 3 or higher with a "reasonable possibility" of being related to DAAs (ABT-493/ABT-530);
- Treatment-emergent AEs leading to discontinuation of study drug;
- DAA-related treatment-emergent AEs leading to discontinuation of study drug;
- Serious treatment-emergent AEs leading to discontinuation of study drug;
- Treatment-emergent AEs leading to interruption of study drug;
- Treatment-emergent AEs leading to death.

For all treatment-emergent AEs (at the SOC and preferred term level), risk differences will be calculated for the DB active arm (Arm A) versus placebo (Arm B). The risk difference will be calculated as the percentage of subjects in Arm A with the event minus the percentage of subjects in Arm B with the event. The risk differences will be included on the summaries of AEs during the DB Treatment Period.

A listing of treatment-emergent adverse events grouped by SOC and preferred term with subject numbers will be created.

Adverse Events by Preferred Term

The following summaries of AEs tabulated according to preferred term and sorted by overall frequency in Arm A for the DB active and DB placebo groups and by frequency for the OL active group will be generated:

- Treatment-emergent AEs (will also be presented for the set of HCV/HIV co-infected subjects within the populations/groups specified in Section 11.1);
- Treatment-emergent AEs with a "reasonable possibility" of being related to DAAs (ABT-493/ABT-530);
- Serious treatment-emergent AEs;
- Serious treatment-emergent AEs with a "reasonable possibility" of being related to DAAs (ABT-493/ABT-530);
- Treatment-emergent AEs of Grade 3 or higher;
- Treatment-emergent AEs of Grade 3 or higher with a "reasonable possibility" of being related to DAAs (ABT-493/ABT-530).

These summaries also will include the risk difference defined earlier and the 2-sided 95% CI on the risk difference using the Wilson score method for a difference in proportions.¹²

Adverse Events by Maximum Severity Grade Level

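### Double-blind adverse events are counted about 30 days longer in Arm A than in Arm B subjects who go on to open-label drug, so the crude risk differences lean upward for active treatment

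*SAP*

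**What the plan says.** - **Arm A window.** SAP 11.2.1 counts an event in the double-blind period if its onset is "after the first dose of active study drug and no more than 30 days after the last dose of study drug". Protocol 8.1.5.1 has the same rule: "after initiation of active study drug through 30 days after the last dose of active study drug".
- **Arm B window.** SAP 11.2.1 and Protocol 8.1.5.1 both stop the placebo count "through 30 days after the last dose of placebo and prior to OL Day 1 (if applicable").
- **When OL Day 1 falls.** Study drug is dispensed at the final double-blind visit, and Protocol 5.1.3 states: "Administration of ABT-493/ABT-530 will start the next day (OL Day 1").
- **Durations.** SAP 4.2: "Treatment experienced GT3-infected subjects will receive 16 weeks of treatment", while "all other subjects will receive 8 weeks of treatment in the DB and/or OL Treatment Period".
- **Comparison.** SAP 11.2.2: "risk differences will be calculated for the DB active arm (Arm A) versus placebo (Arm B"), at system organ class (SOC) and preferred-term level, as one percentage minus the other. A 95% Wilson interval is added in the preferred-term tables only.
- **Status of the extra days.** Protocol 5.1.4 starts the Post-Treatment Period the day after the last active dose. Protocol 8.1.5 says data from that period will be summarised without comparisons. Protocol 5.1.2 un-blinds treatment at the final double-blind visit.

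**The concern.** The two percentages being subtracted come from observation periods of different length. Protocol 6.1.4 collects all adverse events for 30 days after dosing, so the Arm A tail does yield events. An Arm B subject who starts open-label drug has no matching tail, because anything after OL Day 1 belongs to active treatment. Extra days can raise Arm A's percentage and cannot lower it, so the direction of the bias is fixed.

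Two further points make the tail a poor basis for comparison. Its events are reported, graded and judged for drug-relatedness after un-blinding, while nearly all the placebo events they are set against come from the blinded period. And they are Post-Treatment data, on which Protocol 8.1.5 rules out comparisons, yet SAP 11.2.2 presents them as double-blind period results.

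At stake is how the randomised adverse-event tables are read. Fisher's exact tests were dropped (SAP 12.1, items 16 and 17), so the risk difference is the only planned between-arm summary of adverse events.

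**Working it through.** **Plan's own figure.** None. The documents state the rules but no window lengths, so the lengths below are derived.

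**Step 1: windows.**
- 8-week regimen: Arm A 8 × 7 + 30 = 86 days; Arm B 8 × 7 = 56 days; ratio 86/56 = 1.536.
- 16-week regimen: Arm A 112 + 30 = 142 days; Arm B 112 days; ratio 142/112 = 1.268.

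The 8-week figures dominate. Only treatment-experienced GT3 subjects get 16 weeks, and GT3 as a whole is weighted at 7% of enrolment (SAP Table 3).

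**Step 2: expected difference with no drug effect.** Assume a constant hazard, equal in both arms. If pB is the placebo risk over 56 days, Arm A is expected to show pA = 1 − (1 − pB)^(86/56).

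Example: pB = 5% gives pA = 1 − 0.95^1.536 = 7.57%, a difference of +2.6 points.

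Variant with the hazard halved in the 30-day tail: the exponent becomes 1 + 0.5 × 30/56 = 1.268. At 5% this gives 6.30%, or +1.3 points.

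**Step 3: how often the interval excludes zero.** Simulation with 336 v 168 subjects (SAP Table 1), 40,000 runs per case, Wilson score interval for a difference. The placebo risks are assumptions.

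| Placebo risk | Arm A, equal hazard | Difference (points) | CI above 0 | Difference, half tail hazard | CI above 0 |
|---|---|---|---|---|---|
| 1% | 1.53% | +0.5 | 1.5% | +0.3 | 0.5% |
| 5% | 7.57% | +2.6 | 16% | +1.3 | 6% |
| 10% | 14.94% | +4.9 | 32% | +2.5 | 11% |
| 30% | 42.18% | +12.2 | no CI specified | +6.4 | no CI specified |
| 50% | 65.51% | +15.5 | no CI specified | +8.5 | no CI specified |

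The last two rows stand for any-event percentages or large SOCs, for which SAP 11.2.2 specifies no interval.

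**Step 4: 16-week regimen.** The exponent is 142/112 = 1.268, so 5% over 112 days becomes 6.3% (+1.3) and 10% becomes 12.5% (+2.5).

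**Step 5: subjects who differ in proneness to events.** With gamma frailty of variance 1 (an illustration), survival is 1/(1 + H), with H scaled by 1.536.
- At 50%: H = 1, so pA = 1 − 1/2.536 = 60.6%, or +10.6 points instead of +15.5.
- At 5%: H = 1/0.95 − 1 = 0.0526, so pA = 1 − 1/1.0808 = 7.5%, or +2.5 points instead of +2.6.

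This trims the large percentages and barely touches preferred terms.

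**Step 6: after a common cut-off.** With 56 v 56 or 112 v 112 days, the expected difference under no drug effect is 0. The interval then lies above zero in 1.6% of runs at 5% risk and 2.1% at 10%.

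**The case against.** Cutting Arm B at OL Day 1 is unavoidable, a 30-day tail is a sensible descriptive summary, and both definitions are stated openly. The comparison is descriptive: no success criterion or multiplicity step uses it, and the primary endpoints set Arm A against historical thresholds. The bias cannot hide harm. All of this stands, and it limits the severity. It does not justify subtracting percentages from unmatched windows: an upward lean can create apparent drug effects, and it also lets a real one be put down to longer follow-up.

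Constant hazard is probably generous. Protocol Appendix C has one scheduled visit in the tail (PT Week 4), against Weeks 1, 2, 4 and 8 during dosing, so ascertainment may be thinner. That stands too, and is why the half-hazard figures are given.

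A reader might take a 50% any-event rate, attach an interval and infer a 92% chance of a false signal, which is what the simulation gives for that case. The documents do not support this as a planned result. The overview table in SAP 11.2.2 specifies counts and percentages only, and intervals are specified only by preferred term. The protocol's own frequencies (Section 3.0, earlier studies of active drug) describe the commonest events as occurring in more than 5% of subjects, and serious events in 1.5%. The 5% to 10% rows are therefore the relevant ones for the planned intervals.

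**Conclusion.** The between-arm adverse-event risk differences are biased upward for Arm A by construction. The direction follows from the definitions. The size rests on assumed placebo rates and on equal hazards in the two arms: about +1.3 to +2.6 points for a preferred term at 5%, and +2.5 to +4.9 points at 10%, with the Wilson interval above zero in roughly 6% to 16% and 11% to 32% of trials. Percentages of 30% to 50% would shift by about 6 to 16 points, without a specified interval.

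A reader might infer that the whole safety comparison is compromised. It is not:
- Rare events move little (1.0% to about 1.5%).
- Events leading to discontinuation or interruption of study drug are essentially unaffected.
- Laboratory toxicity grades are compared during treatment in both arms (SAP 11.3.2).
- Arm B subjects who never enter open-label treatment keep their 30 days. Those who stop placebo early keep up to 30 days before OL Day 1.

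This should be fixed; it is not critical to the trial's conclusions.

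**What to change.** In SAP 11.2.1, add a common comparison window and compute the risk differences and intervals of SAP 11.2.2 on it. Count onset from the first double-blind dose to the same on-treatment cut-off in both arms. The cut-off could be the last double-blind dose. It could also follow the SAP's own on-treatment convention (SAP 6.1.2 and Table 4): DB Study Drug End Day 2 and before OL Day 1. If the latter is used, cap Arm A at the final scheduled double-blind visit as well, since otherwise Arm A completers regain two days that Arm B does not have.

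Keep the 30-day tables as by-arm descriptions without a between-arm difference. Because Protocol 8.1.5.1 carries the same window, log the change in SAP 12.1.

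Cost: one definition and one added set of tables, with no new data. Arm A events in the post-dosing tail leave the comparison but stay in the Arm A summary.

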11.2.2 Tabulations of Treatment-Emergent Adverse Events

The number and percentage of subjects with treatment-emergent AEs will be tabulated by primary MedDRA System Organ Class (SOC) and preferred term. The SOCs will be

presented in alphabetical order, and the preferred terms will be presented in alphabetical order within each SOC.

Subjects reporting more than one AE for a given preferred term will be counted only once for that term (most severe/highest grade incident for the severity tables and most related incident for the relationship tables). Subjects reporting more than one AE within a SOC will be counted only once for that SOC. Subjects reporting more than one AE will be counted only once in the overall total.

AEs will be presented for the following 3 groups, separately: 1) DB active (Arm A during the DB Treatment period), 2) DB placebo (Arm B during the DB Treatment Period), and 3) OL active (Arm B during the OL period).

Adverse Event Overview

An overview of AEs will be presented consisting of the number and percentage of subjects experiencing at least one event for each of the following AE categories; this overview will also be presented for the set of HCV/HIV co-infected subjects within the populations/groups specified in Section 11.1:

- Any treatment-emergent AE;
- Treatment-emergent AEs with a "reasonable possibility" of being related to DAAs (ABT-493/ABT-530);
- Treatment-emergent AEs of Grade 3 or higher;
- Treatment-emergent AEs of Grade 3 or higher with a "reasonable possibility" of being related to DAAs (ABT-493/ABT-530);
- Serious treatment-emergent AEs;
- Serious treatment-emergent AEs with a "reasonable possibility" of being related to DAAs (ABT-493/ABT-530);
- Treatment-emergent AEs leading to discontinuation of study drug;
- DAA-related treatment-emergent AEs leading to discontinuation of study drug;
- Serious treatment-emergent AEs leading to discontinuation of study drug;

- Treatment-emergent AEs leading to interruption of study drug;
- Treatment-emergent AEs leading to death;
- Deaths.

Adverse Events by SOC and Preferred Term

The following summaries of AEs by SOC and preferred term will be generated:

- Treatment-emergent AEs (will also be presented for the set of HCV/HIV co-infected subjects within the populations/groups specified in Section 11.1);
- Treatment-emergent AEs with a "reasonable possibility" of being related to DAAs (ABT-493/ABT-530);
- Serious treatment-emergent AEs;
- Serious treatment-emergent AEs with a "reasonable possibility" of being related to DAAs (ABT-493/ABT-530);
- Treatment-emergent AEs of Grade 3 or higher;
- Treatment-emergent AEs of Grade 3 or higher with a "reasonable possibility" of being related to DAAs (ABT-493/ABT-530);
- Treatment-emergent AEs leading to discontinuation of study drug;
- DAA-related treatment-emergent AEs leading to discontinuation of study drug;
- Serious treatment-emergent AEs leading to discontinuation of study drug;
- Treatment-emergent AEs leading to interruption of study drug;
- Treatment-emergent AEs leading to death.

For all treatment-emergent AEs (at the SOC and preferred term level), risk differences will be calculated for the DB active arm (Arm A) versus placebo (Arm B). The risk difference will be calculated as the percentage of subjects in Arm A with the event minus the percentage of subjects in Arm B with the event. The risk differences will be included on the summaries of AEs during the DB Treatment Period.

A listing of treatment-emergent adverse events grouped by SOC and preferred term with subject numbers will be created.

Adverse Events by Preferred Term

The following summaries of AEs tabulated according to preferred term and sorted by overall frequency in Arm A for the DB active and DB placebo groups and by frequency for the OL active group will be generated:

- Treatment-emergent AEs (will also be presented for the set of HCV/HIV co-infected subjects within the populations/groups specified in Section 11.1);
- Treatment-emergent AEs with a "reasonable possibility" of being related to DAAs (ABT-493/ABT-530);
- Serious treatment-emergent AEs;
- Serious treatment-emergent AEs with a "reasonable possibility" of being related to DAAs (ABT-493/ABT-530);
- Treatment-emergent AEs of Grade 3 or higher;
- Treatment-emergent AEs of Grade 3 or higher with a "reasonable possibility" of being related to DAAs (ABT-493/ABT-530).

These summaries also will include the risk difference defined earlier and the 2-sided 95% CI on the risk difference using the Wilson score method for a difference in proportions.¹²

Adverse Events by Maximum Severity Grade Level

Treatment-emergent AEs and DAA-related treatment-emergent AEs will be summarized by maximum severity grade level of each preferred term. Each AE will be assigned a grade level (Grade 1, 2, 3, 4, or 5) by the investigator. If a subject has an AE with unknown severity, then the subject will be counted in the severity grade level category of "unknown," even if the subject has another occurrence of the same event with a severity present. The only exception is if the subject has another occurrence of the same AE with the highest grade level (Grade 5). In this case, the subject will be counted under the "Grade 5" category.

Adverse Events by Maximum Relationship

Treatment-emergent AEs also will be summarized by maximum relationship of each preferred term to study drug (DAAs), as assessed by the investigator. If a subject has an AE with unknown relationship, then the subject will be counted in the relationship category of "unknown," even if the subject has another occurrence of the same event with a relationship present. The only exception is if the subject has another occurrence of the same AE with a relationship assessment of "Reasonable Possibility." In this case, the subject will be counted under the "Reasonable Possibility" category.

Adverse Events of Special Interest

The AEs of special interest include the following:

"Hepatic Decompensation and Hepatic Failure" defined by the Product MedDRA Query (PMQ);

"Hepatocellular Carcinoma" defined by the MedDRA preferred terms of hepatocellular carcinoma, hepatic neoplasm, hepatic cancer, hepatic cancer recurrent, and hepatic cancer metastatic.

For the hepatic decompensation/hepatic failure AE of special interest, the number and percentage of subjects experiencing at least one treatment-emergent AE in the search will be presented by SOC and preferred term and across all SOCs/preferred terms. In addition, a by-subject listing of treatment-emergent AEs meeting the search criterion will be provided.

For the hepatocellular carcinoma AE of special interest, a by-subject listing of all post-baseline (i.e., including both treatment-emergent and non-treatment emergent) AEs meeting the search criterion will be provided.

Adverse Events by HIV-1 ART Regimen

For the HCV/HIV co-infected subjects who were on HIV-1 ART at initiation of DB study drug, treatment-emergent AEs also will be summarized for the subgroups defined by the HIV-1 ART regimen (e.g., RAL, DTG, RPV) the subjects were receiving at DB study drug initiation. For each HIV-1 ART regimen, the number and percentage of subjects experiencing treatment-emergent AEs will be tabulated according to SOC and preferred term.

AIDS-Associated Opportunistic Infections

The number and percentage of subjects experiencing treatment-emergent AIDS-associated OIs will be tabulated according to SOC and preferred term for the HCV/HIV co-infected subjects (determined at Screening). Subjects reporting more than one AIDS-associated OI for a given preferred term will be counted only once for that term. Subjects reporting more than one AIDS-associated OI within a SOC will be counted only once for that SOC. Subjects reporting more than one AIDS-associated OI will be counted only once in the overall total.

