### 6.1.3 Relationship to Study Drug

The investigator will use the following definitions to assess the relationship of the AE to the use of study drug:

Reasonable Possibility	An AE where there is evidence to suggest a causal relationship between the study drug and the AE.
No Reasonable Possibility	An AE where there is no evidence to suggest a causal relationship between the study drug and the AE.

For causality assessments, events assessed as having a reasonable possibility of being related to the study drug will be considered "associated." Events assessed as having no reasonable possibility of being related to study drug will be considered "not associated." In addition, when the investigator has not reported a causality or deemed it not assessable, AbbVie will consider the event associated.

[figure not shown]
If an investigator's opinion of no reasonable possibility of being related to study drug is given, an "Other" cause of the event must be provided by the investigator for the serious adverse event.

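### SAP 11.2.2 lets an ungraded record displace a known Grade 1 to 4 in the maximum-severity tables, and classes missing causality as unknown where protocol 6.1.3 treats it as associated

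*SAP*

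**What the plan says.** **Causality.** Protocol 6.1.3 gives a rule for gaps: "when the investigator has not reported a causality or deemed it not assessable, AbbVie will consider the event associated". SAP 11.2.2, under Adverse Events by Maximum Relationship, gives a different one: "If a subject has an AE with unknown relationship, then the subject will be counted in the relationship category of" unknown. It then adds: "The only exception is if the subject has another occurrence of the same AE with a relationship assessment of" Reasonable Possibility, in which case the subject is counted as related. Most of the drug-related overview rows and summaries in the same section are defined by a reasonable-possibility rating; a few are labelled DAA-related.

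**Severity.** SAP 11.2.2, under Adverse Events by Maximum Severity Grade Level, says: "If a subject has an AE with unknown severity, then the subject will be counted in the severity grade level category of" unknown. A graded record of that event does not prevent this, with one exception: a record at Grade 5.

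**The general counting rule.** Protocol 8.1.5.1 counts a subject once per preferred term, "using the event with the most severe grade for the severity grade tables and the most related event for the relationship" tables. The opening of SAP 11.2.2 says the same: "most severe/highest grade incident for the severity tables and most related incident for the relationship tables".

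**Disclosure.** SAP 12.1 lists 21 changes from the protocol. Items 16 and 17 alter the adverse-event tables, but no item mentions missing grade or missing causality.

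**The concern.** Two rules for incomplete records depart from the protocol without being declared.

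For causality, the protocol resolves a gap toward the drug. The SAP puts it in a separate class that appears only in the maximum-relationship table. The overview and the related-serious, related Grade 3 or higher and DAA-related discontinuation tables have no unknown row, so an event with no causality rating would not appear in them.

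For severity, one ungraded record is enough to take a subject with a documented Grade 3 or 4 event out of that grade in the maximum-severity table. Repeat records under one term are to be expected, because protocol 6.1.1.1 asks for a worsening event to be entered as a new one.

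Safety is part of the primary objective (protocol 4.1). Related and high-grade categories may hold few subjects, where a shift of one matters. The causality rule also runs against the SAP's practice elsewhere: incomplete onset dates are presumed treatment-emergent (11.2.1), and SVR data still missing after imputation count as failure (6.3).

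**Working it through.** The plan states no figure to reproduce. The check applies each rule to every combination of records that one subject can have under one preferred term, taking records singly and in pairs.

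**Severity.** Inputs: the missing-grade rule and the highest-grade rule, both in SAP 11.2.2, and the highest-grade rule in protocol 8.1.5.1. The two rules agree whenever both records are graded. With an ungraded record:

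| Records | SAP missing-grade rule | Highest recorded grade |
|---|---|---|
| Grade 1 + ungraded | unknown | Grade 1 |
| Grade 2 + ungraded | unknown | Grade 2 |
| Grade 3 + ungraded | unknown | Grade 3 |
| Grade 4 + ungraded | unknown | Grade 4 |
| Grade 5 + ungraded | Grade 5 | Grade 5 |
| ungraded only | unknown | none available |

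The rules differ in the first four rows.

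*Reach.* The missing-grade rule is written for the maximum-severity summaries (all treatment-emergent events, and DAA-related ones). The overview counts subjects with at least one event of Grade 3 or higher, and separate Grade 3 or higher summaries follow by system organ class and by preferred term. The rule is not written for these, so a known Grade 3 or 4 record still counts there.

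**Causality.** Inputs: the missing-relationship rule in SAP 11.2.2 and the classification rule in protocol 6.1.3. RP is reasonable possibility and NRP is no reasonable possibility.

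| Records | SAP maximum-relationship table | Any RP record? | Protocol 6.1.3 |
|---|---|---|---|
| missing | unknown | no | associated |
| missing + missing | unknown | no | associated |
| NRP + missing | unknown | no | associated |
| RP + missing | RP | yes | associated |
| NRP | NRP | no | not associated |

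The first three rows conflict. With no RP record, nothing qualifies the subject for a table defined by RP. A missing rating displaces only NRP, never RP.

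**Scale.** Planned arm sizes are in SAP Table 1. One subject is 1/336 = 0.298%, or 0.30 percentage points, in Arm A, and 1/168 = 0.595%, or 0.60 points, in Arm B.

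**The case against.** **The missing-grade rule fills a gap.** The general rule is silent on ungraded records. With one record ungraded, the true maximum is uncertain unless another is Grade 5, and showing Grade 1 for a Grade 1 plus ungraded subject assumes the ungraded event was no worse. The uncertainty is real and is the reason for a footnote. It does not justify discarding a documented grade: the highest recorded grade is what both documents ask for, and a known Grade 3 or 4 is a valid lower bound.

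**The protocol bars imputation.** Protocol 8.1 rules out imputing safety data, and the SAP's maximum-relationship table reports the investigator's assessment, so 6.1.3 could be read as a sponsor classification kept apart from the tables. But 6.1.3 is a specific classification rule for adverse events. It is not confined to serious ones; the sentence on giving another cause does carry that limit. Reporting the highest recorded grade imputes nothing.

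**The exclusion is not written down.** The SAP never says in words that missing-causality events stay out of the drug-related tables. This stands as a caveat. The inference is nonetheless firm: a separate unknown class would have no purpose if such events were already counted as related, and no recoding rule appears. These events remain in the all-event tables and, where they qualify, in the serious and Grade 3 or higher tables and the listings.

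**Such records should be rare.** Protocol 6.1 and 6.1.2 require investigators to record relationship and severity, and data are cleaned before lock. That limits the likely size, but the rule exists for whatever remains.

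**Conclusion.** The point holds in two limited parts. In the maximum-severity tables, a missing grade displaces a known Grade 1 to 4 of the same term, against the highest-grade rule in both documents. Missing causality goes to an unknown class, and no SAP rule carries it into the drug-related tables and overview rows, against protocol 6.1.3. Neither departure is declared in SAP 12.1.

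A reader might infer three stronger things that the documents do not support:

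- That known Grade 3 or 4 events vanish from the safety report. They still count in the Grade 3 or higher tables.
- That a missing causality rating overrides a known related or severe event. It displaces only a no-reasonable-possibility rating.
- That a number of affected subjects can be given. The documents state no rate of missing grade or causality. The severity effect also needs a second, graded record of the same term in the same subject.

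The size is therefore one subject per affected case, 0.30 points in Arm A or 0.60 in Arm B at the planned arm sizes, with an unknown total. The primary efficacy conclusions are unaffected. The causality part rests on the inference that no unstated recoding is done before tabulation.

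**What to change.** Amend SAP 11.2.2 in two places:

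1. Count events with missing or not-assessable causality as related in every drug-related table and overview row, as protocol 6.1.3 provides, with a footnote giving the number so classified in each arm.
2. In the maximum-severity tables, show the highest known grade for the preferred term. Keep unknown for terms with no graded record, and footnote the subjects who also have an ungraded record.

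If the sponsor keeps either present rule, list it in SAP 12.1 as a departure from the protocol, with the reason.

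The cost is SAP wording and two table footnotes, with no change to data collection. The downside is that drug-related counts may rise slightly; the footnote lets a reader see how much of that comes from missing ratings.
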